3.9.3.2. Secondary Endpoints

- Change from baseline to Weeks 24 and 48 in Hb, LDH, indirect bilirubin, and reticulocyte count

- Change from baseline to 24 weeks in cerebral blood flow as measured by the TAMM TCD velocity
- Time to initial Hb response, defined as change from baseline in Hb $> 1\text{ g/dL}$
- Whole blood and plasma voxelotor PK (C_{\max} , AUC, $t_{1/2}$), and percent Hb occupancy
- Proportion of participants with normal TCD flow velocity ($< 170\text{ cm/sec}$ by nonimaging TCD or $< 155\text{ cm/sec}$ by TCDi) at 48 weeks
Incidence of stroke and VOC during the study

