10.3.3. Efficacy Data

The laboratory parameters (Hb, reticulocyte count, erythropoietin, LDH and indirect bilirubin) and cerebral blood flow as measured by TAMM TCD velocity (Parts B and C only) will be listed and summarized at each visit for observed values and changes from baseline using appropriate descriptive statistics. Time to initial Hb response will be summarized descriptively (Parts C and D). The proportion of participants with normal TCD at 48 weeks will be summarized (Part C).

For Parts C and D, the incidence of stroke and annualized incidence of VOC will be summarized descriptively.

For Part B only, change from Baseline to Weeks 21–24 in the SCDSM TSS; for each participant, the TSS will be computed as follows: The Baseline TSS is the average of the score during the 35-day Screening period; during the treatment period, the TSS is the average score each 4-week period on treatment. The 4-week periods are Weeks 1–4, 5–8, 9–12, 13–16, 17–20 and 21–24 (and follows similarly for participants whose participation exceeds 24 weeks). Change from baseline in the TSS and the proportion of days with SCD symptom exacerbation will be summarized using descriptive statistics (Part B).

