## **6. ANALYSIS POPULATIONS**

### **6.1. Efficacy Evaluable Population**

All subjects who received at least one dose of study drug will be included in the Efficacy Evaluable population (EE). The EE population will be the primary population for the efficacy analyses.

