## **7. STATISTICAL METHODS**

Statistical analyses will be performed using SAS® Version 9.4 or higher.

Data summaries will be presented as: 4-11 years, 12-17 years and overall (4-17 years) age groups.

Continuous variables will be descriptively summarized using number of subjects (n), mean, standard deviation (SD), median, quartiles, minimum, maximum, and, as appropriate, 95% confidence intervals. Categorical variables will be descriptively summarized by presenting the number (frequency) and percentage in each category.

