## 7.2. Efficacy Analysis

Efficacy data will be summarized using the EE population.

The primary endpoint for Part C is change from baseline to 48 weeks in cerebral blood flow as measured by the TAMM TCD velocity.

TCD flow velocity will be summarized descriptively at Week 24 and Week 48 for observed values and absolute changes. TCD is presented as TCD (non-imaging) in the summary table. TCDi (imaging) has been normalized to TCD (non-imaging) by adding 15 cm/sec.

The proportion of subjects with normal TCD flow velocity (< 170 cm/sec by nonimaging TCD or < 155 cm/sec by TCDi) at 48 weeks will be summarized descriptively for the overall population and by Baseline TCD category (Normal, Conditional).

Hb response, defined as an increase in Hb > 1 g/dL, will be summarized descriptively at Week 24 and Week 48. Subjects who drop-out early or do not have a Week 24 or Week 48 visit, are not included in the analysis for Hb response at each of the respective visits. Additional response assessment at each visit will be summarized descriptively. No missing data imputation or adjustment for RBC transfusion will be performed for this endpoint.

Additionally, Hb response at Week 24 and Week 48 will be summarized using the treated population. All subjects treated will be included in the denominator for Hb response.

For subjects who have had a Hb response at least 1 visit, the time to the first response will be summarized descriptively.

Hematology parameters (hemoglobin, reticulocyte count, indirect bilirubin, and LDH) and in addition to each visit for observed values and changes (absolute and percent) from baseline using appropriate descriptive statistics. If indirect bilirubin is missing and direct and total bilirubin are collected, indirect can be calculated as:

$$\text{Indirect Bilirubin} = \text{Total Bilirubin} - \text{Direct Bilirubin}.$$

To evaluate the effect of voxelotor on the incidence of stroke and vaso-occlusive crisis (VOC), the annualized incidence rate will be summarized and 95% CI provided.

Efficacy assessment will be summarized by subgroups defined by subjects' sex, baseline HU use, and 4-11 age group (4 to 7 years and 8 to 11 years). Efficacy assessments to be summarized by subgroup include Hb response and change from baseline for hematology parameters and TCD flow velocity.

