### 4.2. Secondary

- Whole blood and plasma voxelotor PK (maximum blood concentration [ $C_{max}$ ], area under the concentration-time curve [AUC], terminal elimination half-life [ $t_{1/2}$ ], if appropriate) and percent hemoglobin (Hb) occupancy
- Change from baseline to Week 24 and Week 48 in Hb, lactate dehydrogenase (LDH), indirect bilirubin, and reticulocyte count
- Time to initial Hb response, with Hb response defined as change from baseline in Hb  $> 1\text{g/dL}$ 
  - Time to initial Hb response is defined as time from first dose of study treatment to first occurrence of change from baseline in Hb  $> 1\text{g/dL}$
- Incidence of stroke and VOC during the study
- In addition to the protocol-specified secondary endpoints, Hb response (defined as a change from baseline in Hb  $> 1\text{g/dL}$ ) will be assessed at both Week 24 and Week 48.

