## 7. ANALYSIS POPULATIONS

### 7.1. Efficacy Evaluable Population

All subjects who receive at least one dose of study drug will be included in the Efficacy Evaluable population (EE). All efficacy analyses will be based on the EE population.

In this study (GBT440-007 Part D), the EE population is the same as the Safety Population (see Section 7.2).

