## 8.2. Efficacy Analysis

All efficacy data will be summarized using the EE population.

Hematology and hemolysis parameters (hemoglobin, reticulocyte count, indirect bilirubin, and LDH) will be summarized at Week 24 and Week 48 in addition to each visit for observed values and changes (absolute and percent, as appropriate) from baseline using appropriate descriptive statistics. If indirect bilirubin is missing and direct and total bilirubin are collected, indirect can be calculated as:

$$\text{Indirect Bilirubin} = \text{Total Bilirubin} - \text{Direct Bilirubin}.$$

Hb response, defined as an increase in Hb  $> 1$  g/dL, will be summarized descriptively at Week 24 and Week 48 with 95% confidence intervals provided for the response rates. Subjects who drop-out early or do not have a Week 24 or Week 48 assessment, are not included in the analysis for Hb response. Additional response assessments at each visit will be summarized descriptively. No missing data imputation or adjustment for RBC transfusion will be performed for this endpoint.

Additionally, Hb response at Week 24 and Week 48 with 95% confidence intervals will be summarized using the treated population. All subjects treated will be included in the denominator for Hb response, and subjects without a Week 24 or Week 48 assessment will be counted as non-responders at each relevant timepoint.

For subjects who had a Hb response at least 1 visit, the time to the first response will be summarized descriptively (ie, median, first quartile, third quartile, and range).

The annualized incidence rates for VOC and stroke and the associated 95% CIs will be presented. Annualized rate is defined as the total number of events divided by total person years. Total person-years is defined as the sum of subject treatment period in years which covers the time from first dose to last dose. VOC is defined based on clinical review of adverse event MedDRA preferred terms (eg, sickle cell anemia with crisis, acute chest syndrome, and pneumonia).

Exploratory analysis for change from baseline to Weeks 24 and 48 in height, weight, and head circumference, will be summarized using continuous descriptive statistics at each visit.

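### In Parts C and D, time to initial Hb response is summarised among responders only, so no planned output gives cumulative first response over all treated children (minor, cheap improvement)

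*SAP*

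**What the plan says.** **Endpoint.** Protocol 3.9.3.2 (Part C) lists "Time to initial Hb response, defined as change from baseline in Hb" above 1 g/dL as a secondary endpoint, and 3.9.4.2 does the same for Part D. The Part D SAP (4.2) adds the time origin: "Time to initial Hb response is defined as time from first dose of study treatment to first occurrence of change from baseline" in Hb beyond that threshold. None of these limits the endpoint to children who respond.

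**Population.** Both SAPs define the EE population as everyone with at least one dose. Part C SAP 6.1: "The EE population will be the primary population for the efficacy analyses". Part D SAP 7.1: "All efficacy analyses will be based on the EE population".

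**Analysis of the endpoint.** Part C SAP 7.2: "For subjects who have had a Hb response at least 1 visit, the time to the first response will be summarized descriptively". Part D SAP 8.2: "For subjects who had a Hb response at least 1 visit, the time to the first response will be summarized descriptively", with median, quartiles and range named. Protocol 10.3.3 asks only for a descriptive summary. No document gives a censoring rule, a cumulative estimate, or a rule for non-responders and early leavers in this endpoint.

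**Planned alongside it.**
- Part C SAP 7: "Continuous variables will be descriptively summarized using number of subjects (n), mean, standard deviation (SD), median, quartiles, minimum, maximum". Part D SAP 8 also includes n, so the number of responders will be shown.
- Both SAPs plan Hb response at each visit.
- Both plan Hb response at Weeks 24 and 48 twice, once on observed cases and once with all treated children in the denominator. Part D says explicitly that a missing assessment counts as non-response.

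**The concern.** The summarised group is selected on the outcome, so its median answers how soon responders responded. The endpoint, applied to everyone dosed, asks how soon treated children respond. A child who never responds, or who leaves before responding, does not enter the summary at all. A reported median of, say, 4 weeks is easily read as applying to treated children, which this output cannot support. What is at stake is the description of a secondary endpoint in an uncontrolled study. No test or error rate depends on it.

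**Working it through.** The plan states no figure for this endpoint, so there is nothing to reproduce. The check is a comparison of the planned outputs, then an illustration.

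**What each planned output gives**

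| Output | All treated children? | First response by a visit? |
|---|---|---|
| Time to first response | No, responders only | Timing among responders only |
| Hb response at each visit | Not stated (observed cases for the main Week 24 and 48 analysis) | No, status at that visit |
| All-treated response, Weeks 24 and 48 | Yes | No, status at that visit |
| Number of responders ÷ number treated | Derivable by the reader | Crude ever-response, no timing; early leavers count as non-responders |

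**Inputs.** Post-dose Hb visits are at Weeks 2, 4, 8, 12, 16, 20, 24, 36 and 48 (Protocol Appendices 5 and 7). Baseline is the mean of all pre-dose readings (Part C SAP 4, Part D SAP 5), taken here as two. Response share p, onset pattern, dropout and within-subject SD are assumptions.

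**1. Early onset, timing among responders held fixed.** Weights over the nine visits are .30, .25, .15, .10, .06, .05, .04, .03, .02. They cumulate to .30 (Week 2), .55 (Week 4), .70 (Week 8), .80 (Week 12), .86 (Week 16) and 1.00 (Week 48). Responder-only Q1/median/Q3 are therefore Weeks 2/4/12 for every p. The all-treated median is the first visit where p × cumulative weight reaches .50:
- p = .36: maximum .36, not reached
- p = .60: .60 × .80 = .48 at Week 12, .60 × .86 = .516 at Week 16, so Week 16
- p = .75: .75 × .70 = .525, Week 8
- p = .95: .95 × .55 = .5225, Week 4

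**2. Slow onset, constant hazard.** F(t) = 1 − (1 − p)^(t/48). The responder-only median is where F(t)/p first reaches .50; the all-treated median is where F(t) does.

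| p | Responder-only median | All-treated median |
|---|---|---|
| .36 | Week 24 | not reached |
| .60 | Week 20 | Week 48 |
| .80 | Week 16 | Week 24 |
| .95 | Week 12 | Week 12 |

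Here the responder-only median does move with p.

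**3. Dropout** (exponential, independent of response, p = .60, simulated).

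| Dropout by Week 48 | Crude share, slow | Crude share, early | Kaplan-Meier |
|---|---|---|---|
| 10% | 57.0% | 58.8% | 60% |
| 20% | 53.9% | 57.6% | 60% |
| 30% | 50.6% | 56.4% | 60% |

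The gap runs from 60 − 58.8 = 1.2 to 60 − 50.6 = 9.4 points. The responder-only median did not change.

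**4. Limit of any cumulative figure: no drug effect at all.** The change is one reading minus the mean of two, so its SD is s√1.5 for within-subject SD s. P(change > 1 g/dL at one visit) = 1 − Φ(1/(s√1.5)). The chance of at least one crossing over nine visits was simulated.

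| s (g/dL) | One given visit | At least once by Week 48 |
|---|---|---|
| 0.2 | 0.0% | 0.02% |
| 0.3 | 0.3% | 2.6% |
| 0.4 | 2.1% | 13.6% |
| 0.5 | 5.1% | 28.4% |

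**5. Precision.** Exact 95% CI at an observed 50%: 35.5–64.5% (n = 50), 31.3–68.7% (n = 30), 18.7–81.3% (n = 10, the minimum number under 2 years in Protocol 3.1.4).

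**The case against.** The strongest reply is that nothing here is an error. The protocol asks for a descriptive summary and gets one, and the SAP sentences say openly that they cover responders. That stands: a reader might infer that the SAPs depart from the protocol, and they do not.

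A reader might also infer that the plan ignores dropout in Hb response generally. The all-treated analyses at Weeks 24 and 48 rule that out; the gap is confined to time to first response. The by-visit response rates also show onset beyond the responders, which narrows the gap further.

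The dropout gain is modest. It is about 1 to 9 points under an assumption of independent dropout, against CI half-widths of about 14.5 points at n = 50 and 18.7 at n = 30. Protocol 6.2 also keeps most children who stop treatment under assessment. This limits what Kaplan-Meier buys; the main gain is the all-treated denominator.

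Finally, a cumulative figure has its own bias. At a within-subject SD of 0.4 to 0.5 g/dL, chance crossings (13.6% to 28.4%) exceed the dropout gap. RBC transfusion, and in Part D the permitted hydroxyurea titration, can also produce crossings. This stands too, and is why the fix carries caveats.

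**Conclusion.** The point holds as a minor, cheap improvement. In Parts C and D the only planned summary of time to initial Hb response is conditional on responding, and no planned output gives cumulative first response over all treated children or handles dropout for that endpoint.

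That follows from the text alone. The size does not: every magnitude rests on assumed onset, response and dropout rates. It is tempting to conclude that the responder-only median is always blind to the response rate. It is constant only if timing among responders is fixed; under slow onset it moved from Week 24 to Week 12 as the response share rose from 36% to 95%, though it was still earlier than the all-treated median except at 95%.

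**What to change.** In Part C SAP 7.2 and Part D SAP 8.2:

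1. Keep the responder-only summary, label it as such, and print responders n/N treated beside it.
2. Add a Kaplan-Meier estimate over the EE population. Event: first scheduled on-treatment visit with Hb more than 1 g/dL above baseline. All others are censored at their last on-treatment Hb assessment, so that end-of-study and other off-drug readings do not count.
3. Report cumulative first response at Weeks 12, 24 and 48, and the median where reached, with 95% CIs overall and descriptively by age group.
4. Print with it that censoring may be informative; that first response is unconfirmed and rises with the number of visits through measurement variation; that RBC transfusion and, in Part D, hydroxyurea titration can produce crossings; and that it is to be read beside the by-visit response rates, not as a treatment-effect rate.

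The cost is SAP wording and one standard procedure on data already collected. The downside is that the all-treated median may be later or not reached, and the figure cannot be shown without its caveats.

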## 7.3. Safety

All safety analyses will be conducted using the Safety Population.

### 7.3.1. Summary of Exposure

The duration of study drug exposure and actual study drug exposure will be summarized with descriptive statistics.

The number and percentage of subjects who permanently discontinued study drug, and the reason for discontinuation (adverse event (AE) or other) will be summarized. The number and percentage of subjects who missed at least 1 dose of study drug or had at least 1 dose reduction will be summarized. The summary will include the number and percentage of subjects who had a dose reduction or dose missed due to an adverse event or other. Additionally, the number and percentage of subjects will be summarized in categories of number of missed doses and number of dose reductions.

### 7.3.2. Adverse Events

Adverse events reported for subjects participating in this study will be graded using the National Cancer Institute's (NCI) Common Terminology Criteria for Adverse Events (CTCAE), version 4.03. All AEs will be coded using MedDRA (current version).

All adverse events summaries described below will be presented for both non-SCD and SCD-related TEAEs.

Non-SCD-related TEAE summary tables will exclude sickle cell disease (SCD) related events defined as preferred terms of: acute chest syndrome, pneumonia, pneumonia necrotising, sickle cell anemia with crisis, osteonecrosis, and priapism. Additional TEAE tables will summarize the aforementioned SCD related events.

Overall summaries will be presented which includes the number of TEAEs and the number and percentage of subjects who experienced at least one TEAE. The summaries will also include TEAEs Grade 3 or greater, TEAEs possibly/probably related to study drug, TEAEs leading to study drug reduction, TEAEs leading to study drug interruption, TEAEs leading to discontinuation of study drug, serious adverse events (SAEs) and SAEs possibly/probably related to study drug. TEAEs leading to deaths will be summarized together regardless if they are SCD-related as cause of death may include multiple TEAEs.

Additional summaries of TEAEs will be provided showing the number and percentage of subjects who experienced at least one TEAE. These summaries will be presented by system organ class (SOC), preferred term (PT) and maximum severity. If a subject reports the same PT multiple times within the same SOC, that PT will only be counted once within that SOC for that subject. As with the PT, if a subject reports multiple conditions within the same SOC, that SOC will only be counted once for that subject. In the summary, SOC will be listed in ascending alphabetical order; PTs will be listed in order of descending frequency for all subjects within each SOC.

The occurrence of TEAEs possibly/probably related to voxelotor will be tabulated by SOC, PT and maximum severity. Serious adverse events will be presented by system organ class (SOC), preferred term (PT) and maximum severity.

Grouped terms for rash and abdominal pain are summarized by PT.

Adverse events recorded in the eCRF which began prior to first dose of study drug will not be included in the TEAE summary tables.

### **7.3.3. Concomitant Medications**

Concomitant medications will be coded using the World Health Organization (WHO) Drug Dictionary (current version) and summarized to the therapeutic drug class (Anatomical Therapeutic Chemical (ATC) 4 classification) and preferred name.

### **7.3.4. Clinical Laboratory Data**

All hematology and chemistry laboratory assessments were performed by local laboratories.

The following protocol-specified clinical laboratory findings will be summarized using descriptive statistics.

1. Hematology:
  - a. Hemoglobin
  - b. Neutrophils (absolute and %)
  - c. Platelets
  - d. Reticulocyte count (percent)
  - e. WBC

2. Chemistry and Liver Function Tests:

- a. Alkaline phosphatase
- b. ALT
- c. AST
- d. Lactate dehydrogenase (LDH)
- e. Potassium
- f. Indirect bilirubin
- g. Total bilirubin
- h. Serum erythropoietin

Change from baseline and the percent change from baseline will be summarized for the above laboratory results. Analyte units will be converted to SI units.

Subject listings of laboratory data will include a separate listing for clinically significant laboratory results. Urinalysis, coagulation and pregnancy results will be listed only.

**7.3.5. Vital Signs and Physical Exam**

Vital signs, including systolic and diastolic blood pressure, heart rate, respiratory rate, temperature, and weight will be summarized using continuous descriptive statistics at each visit and time point. Change from baseline will also be summarized for each post-baseline visit.

**7.3.6. 12-Lead Electrocardiogram**

Heart rate, PR interval, QRS interval, QT interval, RR interval, and QTcF (Fridericia's) interval will be summarized along with the change from baseline using descriptive statistics at each visit. The average of the 3 ECGs collected will be used in the summary tables.

Additionally, the number and percentage of subjects with QTcF  $\leq$  450 ms,  $>450$  ms to  $\leq$  480 ms,  $>480$  ms to  $\leq$  500 ms, and  $>500$  ms at baseline and as the maximum post-baseline measurement will be summarized. The number and percentage of subjects with maximum increase from baseline where increase in QTcF  $\leq$  30 ms,  $>30$  ms to 60 ms and  $>60$  ms also will be summarized. If the QTcF interval was not collected, the interval will be calculated using the following formula:

$$\text{QTcF} = \text{QT} / (60/\text{HR})^{1/3}$$

**8. PROTOCOL DEVIATIONS**

Important protocol deviations and COVID 19 related deviations will be displayed in a data listing and sorted by age group, subject number, and then by date (where applicable) within each subject number. The type of deviation along with a description and any additional comments about the deviation will be listed.

## 1. GLOSSARY OF ABBREVIATIONS

Abbreviation	Description
AE	Adverse Event
ALT	alanine aminotransferase
AST	aspartate aminotransferase
ATC	Anatomical Therapeutic Chemical
AUC	area under the concentration-time curve
BMI	Body Mass Index
CI	Confidence Interval
cm	Centimeter
CRF	Case Report Form
Cmax	Maximum Blood Concentration
CTCAE	Common Terminology Criteria for Adverse Events
ECG	Electrocardiogram
eCRF	electronic case report form
EE	Efficacy Evaluable
g/dL	gram per deciliter
Hb	Hemoglobin
HbF	hemoglobin – fetal
HbS $\beta^0$ thal	sickle hemoglobin (S) and one beta thalassemia gene ( $\beta^0$ thal)
HbSS	sickle hemoglobin with two sickle cell genes (SS)
HU	Hydroxyurea
kg	Kilogram
kg/m 	kilogram per meter squared
LDH	lactate dehydrogenase
MedDRA	Medical Dictionary for Regulatory Activities
n	number of subjects
NCI	National Cancer Institute
PK	Pharmacokinetic(s)
PT	Preferred Term
RBC	Red Blood Cells
SAE	Serious Adverse Event
SAP	Statistical Analysis Plan

Abbreviation	Description
SAS®	Statistical Analysis Software
SCD	Sickle Cell Disease
SD	Standard Deviation
SI	Systeme International
SOC	System Organ Class
$t_{1/2}$	terminal elimination half-life
TEAE	Treatment-Emergent Adverse Event
VOC	vaso-occlusive crisis
WBC	white blood cell
WHO	World Health Organization

